3.2 Rationale of study design

This randomized, multi-center, patient and investigator blinded, placebo-controlled study is designed to assess the efficacy of LIK066 relative to placebo in patients with NASH.

The completed study will enroll 110 patients who will be randomized in a 2:2:1 ratio to 150 mg daily, 30 mg daily and placebo. However, at the beginning of the study, patients will be enrolled into only two arms: 150 mg daily dose and placebo, randomized at 2:1.

Commercially Confidential Information

In order to maintain the scientific integrity of the study, the investigators and patients will remain blinded to their treatment allocation.

Commercially Confidential Information

the Novartis Clinical Trial Team (CTT) will be unblinded throughout the study.

To ensure that no bias is introduced by imbalance of severity of disease across different arms of the study, patients will be stratified to active or placebo arms on the basis of BMI.

Currently there is no approved pharmacotherapy for patients with NASH. All patients will be encouraged to adhere to local advice regarding diet and exercise regimens. To keep the dietary intake as constant as possible during the study, patients participating in this study will be advised to adhere to American Heart Association (AHA) diet or equivalent if there is a country specific recommended diet.

3.3 Rationale for dose/regimen, route of administration and duration of treatment

The primary efficacy endpoint for dose/exposure-response analysis for LIK066, from previously completed clinical studies, was body weight loss, and other pharmacodynamic endpoints such as urinary and plasma glucose.

Commercially Confidential Information

Of note, in the 12 week study in obese patients, the 150 mg daily dose was generally safe and well tolerated. The primary AE was diarrhea, which did not lead to any discontinuation of treatment or patient withdrawals from the study.

Commercially Confidential Information

Body weight loss is an important factor in therapeutic development for NASH as weight loss through either bariatric surgery or life style modification deters progression of the disease ([Lassailly et al 2015](#), [Vilar-Gomez et al 2015](#)).

Commercially Confidential Information

Furthermore, exposure of LIK066 in non-cirrhotic NASH patients (patient population in this study) is anticipated to be in the range of that observed in previous studies since these patients are not expected to have hepatic dysfunction.

The duration of the study is based on findings in published literature relating to Obeticholic acid and elafibranor ([Mudaliar et al 2013](#); [Neuschwander-Tetri et al 2015](#); [Ratziu et al 2016](#)), which demonstrate that 12 weeks will provide an ample time frame to test biochemical changes likely to result from improvement to the NASH phenotype. In addition observations from other studies with surgical, diet and pharmacotherapy including Novartis' diacylglycerol acyltransferase 1 inhibitor(LCQ908; pradigastat) suggest that 12 weeks is also an adequate timeframe to test an effect on liver fat.

3.4 Rationale for choice of comparator

A placebo will be used as a comparator to provide estimates of net drug effects for efficacy and safety/tolerability assessments.

3.5 Purpose and timing of interim analyses/design adaptations

Commercially Confidential Information

3.6 Risks and benefits

There is no anticipated therapeutic benefit expected for patients participating in this study although a small amount of weight loss may be anticipated. The risk to patients in this trial will be minimized by adherence to the inclusion/exclusion criteria, close clinical monitoring during the treatment periods, and stopping rules outlined in [Section 7.1](#).

Risks of LIK066 administration in human subjects may include the development of gastrointestinal adverse reactions, urinary tract infection, , postural hypotension due to volume depletion, ketoacidosis, renal and hepatic toxicity, changes in calcium homeostasis with subsequent effects on bones, hypoglycemia and genitourinary infections (including necrotizing fasciitis of the genitalia and perineum commonly referred to as Fournier's gangrene (see [Section 9.8.4](#)).

Doses of LIK066 proposed in this study have been tested and deemed safe in healthy subjects. Patients should be monitored closely and treated according to the standard of care if deemed necessary by the principal investigator.

In long-term clinical studies in patients with T2DM with CVD or at high risk for CVD, an increase in cases of lower limb amputation (primarily of the toe) has been observed with the SGLT-2 inhibitor canagliflozin ([Neal et al 2017](#)). No increased risk of lower limb amputations has been reported for other SGLT2 inhibitors. In addition, no lower limb amputations have been seen in LIK066 studies to date, but since this risk may constitute a possible class effect, patients with a higher risk for amputation events should be instructed on routine preventative foot care and maintaining adequate hydration.

LIK066 is considered an aneugen at extremely high doses. With the doses and treatment duration proposed in this study, at least 20-fold exposure multiple is maintained relative to the threshold NOEL exposure for aneugenicity. LIK066 is not anticipated to increase the risk of adverse developmental or reproductive outcomes in humans when administered at the highest planned clinical dose of 150 mg. Women of child bearing potential should be informed that taking the study drug may involve unknown risks to the fetus if pregnancy were to occur during the study and must agree that in order to participate in the study they must adhere to the contraception requirement for the duration of the study ([Section 4.2](#)). If there is any question that the subject will not reliably comply, they should not be entered in the study.

Blood samples will be collected frequently during the study either via venipuncture or cannula. Risks associated with blood collection include pain, swelling and/or bruising at the insertion site of the needle. Although rare, localized clot formation, infections and nerve damage may occur. Lightheadedness and/or fainting may also occur during or shortly after the blood draw.

MRI makes use of powerful magnetic fields and radio waves, which are believed to cause no direct adverse consequences when used within FDA-approved specifications. No MRI contrast will be administered in this study. Thus in principle, MRI scans can be repeated in the same patient as often as necessary. The MRI scanning equipment may cause a feeling of claustrophobia in susceptible persons; therefore, sensitivity to enclosed spaces should be queried at screening. Refer to eligibility criteria ([Section 4.2](#)) to exclude patients who are not suitable candidates for MRI scanning.

3.6.1 Blood sample volumes

Approximately 325 mL of blood is planned to be collected over a period of approximately 22 weeks, from each patient as part of the study. Additional samples required for monitoring of any safety findings would be in addition to this volume. This is not considered to be a risk for this population.

Timings of blood sample collection are outlined in the [Table 8-1 Assessment Schedule](#).

A summary blood log is provided in the Site Operations Manual. Instructions for all sample collection, processing, storage and shipment information will be contained in the Central Laboratory Manual

Commercially Confidential Information

4 Population

Patients with a phenotype consistent with NASH

The study population will be comprised of male and female adult overweight or obese patients with EITHER histologic evidence of NASH on liver biopsy within 2 years prior to randomization and elevated ALT OR phenotypic diagnosis of NASH based on elevated ALT, Type 2 diabetes mellitus by elevated HbA1c and increased BMI; full details are outlined in [Section 4.1](#) (Inclusion criteria). Approximately 110 patients will be randomized in the study. At least 88 subjects are expected to complete the study.

4.1 Inclusion criteria

Patients with a phenotype consistent with NASH, eligible for inclusion in this study must fulfill **all** of the following criteria:

1. Written informed consent must be obtained before any assessment is performed
2. Presence of NASH as demonstrated by ONE of the following:

EITHER

Histologic confirmed NASH based on liver biopsy obtained 2 years or less before randomization with a fibrosis level of F1, F2 or F3, in the absence of a histological diagnosis of alternative chronic liver diseases **AND** ALT \geq 50 IU/L (males) or \geq 35 IU/L (females) at screening.

OR

Phenotypic diagnosis of NASH based on presence of ALL THREE of the following at screening:

- ALT \geq 50 IU/L (males) or \geq 35 IU/L (females) **AND**
 - BMI \geq 27 kg/m² (in patients with a self-identified race other than Asian) or \geq 23 kg/m² (in patients with a self-identified Asian race) **AND**
 - Diagnosis of Type 2 diabetes mellitus by HbA1C: \geq 6.5% and \leq 10%
3. Patients must weigh no more than 150 kg (330 lbs.) to participate in the study. Inclusion of subjects with higher weights up to 200 kg (440 lbs.) may occur if a MRI scanner with a table weight of 200kg (440 lbs.) is available.
 4. Male and female patients 18 years or older (at the time of the screening visit)
 5. Able to communicate well with the investigator, to understand and comply with the requirements of the study.

4.2 Exclusion criteria

Patients with a phenotype consistent with NASH, fulfilling any of the following criteria are not eligible for inclusion in this study:

1. History or presence of other concomitant liver diseases including:
 - Hepatitis B or C virus (HCV, HBV) infection. Patients with history of HCV who attained sustained virologic response more than 3 years prior to screening are **not** excluded.
 - Primary biliary cholangitis (PBC)
 - Primary sclerosing cholangitis (PSC)
 - Alcoholic liver disease
 - Definite autoimmune liver disease or overlap hepatitis
 - Suspected or confirmed Gilbert's syndrome
 - Known bile duct obstruction
 - Suspected or proven hepatocellular cancer

2. History or current diagnosis of ECG abnormalities indicating significant risk of safety for patients participating in the study such as:
 - Concomitant clinically significant cardiac arrhythmias, e.g., sustained ventricular tachycardia, and clinically significant second or third degree AV block without a pacemaker
 - History of familial long QT syndrome or known family history of Torsades de Pointes in a first degree relative.
3. Use of GLP-1 agonists such as liraglutide, exenatide , lixisenatide, albiglutide or dulaglutide; SGLT-2 inhibitors such as canagliflozin, empagliflozin or dapagliflozin; Thiazolidinediones (TZDs) such as pioglitazone; FXR agonists such as obeticholic acid (OCA) and any pharmacologically active weight-loss medications such as lorcaserin prior to 6 weeks of screening visit and up to end of study visit.

Commercially Confidential Information

6. Patients with contraindications to MRI imaging, including:
 - Brain aneurysm clip
 - Implanted neural stimulator
 - Implanted cardiac pacemaker or defibrillator, or presence of intracardiac wires
 - Prosthetic heart valves
 - Cochlear implant
 - Ocular foreign bodies that might be ferromagnetic (e.g., metal shavings)
 - Other implanted medical devices (e.g., insulin pumps)
 - Metal shrapnel or bullets still in the body
 - Severe claustrophobia despite use of anxiolytics
 - Tattoos (as determined by the Investigator and Imager)
 - Weight in excess of MRI machine capacity
 - Joint replacements
7. Inability to reliably quantify alcohol consumption based upon local study physician judgment.
8. Current or history of significant alcohol consumption for a period of more than 3 consecutive months within 1 year prior to screening (significant alcohol consumption is defined as more than 20 g/day in females and more than 30 g/day in males, on average).

Commercially Confidential Information

10. Clinical evidence of hepatic decompensation or severe liver impairment as defined by the presence of any of the following abnormalities:

- Serum albumin < 32 g/L
- INR > 1.3
- Direct bilirubin > 13 mg/L
- ALT or AST > 8× ULN
- Alkaline Phosphatase > 3 × ULN
- History of esophageal varices, ascites or hepatic encephalopathy
- Splenomegaly

Commercially Confidential Information

12. Presence of cirrhosis on liver biopsy or clinical diagnosis of cirrhosis.

Commercially Confidential Information

16. Patients taking medications prohibited by the protocol. See [Section 5.2](#) for further details.

17. For those patients that have had a previous liver biopsy: Significant weight loss (>15%) or change in clinical status (in the opinion of the investigator) since the diagnostic liver biopsy to screening (refer to [Section 4.1 #3](#)).

Commercially Confidential Information

22. History of non-alcohol drug abuse within the 12 months prior to dosing, or evidence of such abuse as indicated by the laboratory assays conducted during screening and baseline.

23. Women of child-bearing potential, defined as all women physiologically capable of becoming pregnant, **unless** they are using basic methods of contraception during dosing and for 5 days (approximately 5 times the terminal half life) after stopping study medication. **Basic contraception methods include:**

- Total abstinence (when this is in line with the preferred and usual lifestyle of the subject. Periodic abstinence (e.g., calendar, ovulation, symptothermal, post-ovulation methods) and withdrawal are not acceptable methods of contraception
- Female sterilization (have had surgical bilateral oophorectomy with or without hysterectomy) or tubal ligation at least six weeks before taking study treatment. In case of oophorectomy alone, only when the reproductive status of the woman has been confirmed by follow up hormone level assessment
- Male sterilization (at least 6 months prior to screening). For female subjects on the study the vasectomized male partner should be the sole partner for that subject
- Barrier methods of contraception: Condom or Occlusive cap.
- Use of oral (estrogen and progesterone), injected or implanted combined hormonal methods of contraception or placement of an intrauterine device (IUD) or intrauterine system (IUS), or other forms of hormonal contraception that have comparable efficacy (failure rate <1%), for example hormone vaginal ring or transdermal hormone contraception. In case of use of oral contraception women should have been stable on the same pill for a minimum of 3 months before taking study treatment.

Women are considered post-menopausal and not of child bearing potential if they have had 12 months of natural (spontaneous) amenorrhea with an appropriate clinical profile (e.g. age appropriate, history of vasomotor symptoms) or have had surgical bilateral oophorectomy (with or without hysterectomy), total hysterectomy or tubal ligation at least six weeks ago. In the case of oophorectomy alone, only when the reproductive status of the woman has been confirmed by follow up hormone level assessment is she considered not of child bearing potential.

Commercially Confidential Information

Commercially Confidential Information

The investigator must ensure that all patients being considered for the study meet the above eligibility criteria.

Patient selection is to be established by checking through all eligibility criteria at screening and baseline. A relevant record (e.g. checklist) of the eligibility criteria must be stored with the source documentation at the study site.

Provided patients meet all other eligibility criteria, patients with a single lab value outside of the allowable range may be considered eligible for enrolment, as long as the abnormal lab value is within 10% of the allowable value. Platelets and eGFR values must always fall inside the allowable range as listed in the inclusion and exclusion criteria.

No additional exclusions may be applied by the investigator, in order to ensure that the study population will be representative of all eligible patients.

5 Restrictions for Study Subjects

For the duration of the study, the subjects should be informed and reminded of the restrictions outlined in this section.

5.1 Contraception requirements

Women of child bearing potential must be informed that taking the study treatment may involve unknown risks to the fetus if pregnancy were to occur during the study, and must agree that in order to participate in the study they must adhere to the contraception requirements specified in [Section 4.2](#) (Exclusion criteria). If there were any question that the patient would not comply reliably, they should not be entered or continue in the study.

Male patients should be informed that if a female partner becomes pregnant while he is enrolled in the study, contact with the female partner will be attempted to request her consent to collect pregnancy outcome information. Please refer to exclusion criteria ([Section 4.2](#)) for details of contraception requirements for the study.

5.2 Prohibited treatment

Use of the treatments displayed in [Table 5-1](#) is NOT allowed after screening.

Table 5-1 Prohibited medication

Medication	Prohibited period
GLP-1 agonists such as liraglutide, exenatide, lixisenatide, albiglutide or dulaglutide	See Exclusion criteria (Section 4.2)
SGLT2 inhibitors such as empagliflozin, canagliflozin, dapagliflozin OR ertugliflozin	See Exclusion criteria (Section 4.2)
Pharmacologically active weight-loss medications (eg. lorcaserin, phentermine/topiramate, bupropion-naltrexone HCL, orlistat)	See Exclusion criteria (Section 4.2)
Treatment with drugs that alter intestinal motility (e.g. erythromycin, metoclopramide, tegaserod, methylnaltrexone, alvimopan, loperamide, diphenoxylate and atropine (Lomotil) and difenoxin and atropine (Motofen))	From 7 days prior to screening to EOS visit
Treatment with drugs that have a high incidence of diarrhea (e.g. Orlistat, Acarbose).	From 7 days prior to screening to EOS visit
Chronic systemic steroid treatment or systemic steroids for > 7 consecutive days for worsening of an underlying condition.	From 4 weeks prior to screening to EOS visit
Treatment with or use of strong inhibitors of CYP3A4/5 including boceprevir, clarithromycin, conivaptan, grapefruit juice, indinavir, itraconazole, ketoconazole, lopinavir, fazodone, nelfinavir, posaconazole, ritonavir, saquinavir, telaprevir, telithromycin, and voriconazole. Strong CYP3A inducers including avasimibe, carbamazepine, phenytoin, rifampin, St. John's wort.	See Exclusion criteria (Section 4.2)
General UGT inhibitors including probenecid and valproic acid.	See Exclusion criteria (Section 4.2)

Table 5-2 Permitted medications if dose is stable (within 25 percent of current dose) for at least 3 months prior to randomization

Medications
Oral anti-diabetic medications such as metformin, sulfonylureas or DPP-4 inhibitors
Insulin*
Beta-blockers and thiazide diuretics
Fibrates, statins, niacin, ezetimibe**
Vitamin E (400-800 mg)***
Thyroid hormone
Psychotropic medications (phenothiazines or second generation antipsychotics)
Estrogen or estrogen containing birth control
*unless adjustment is required due to intercurrent illness; **unless adjustment is required to treat medically significant increases in LDL that have been confirmed upon repeat testing; ***Only applicable for patients taking ≥ 400 IU/day

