LIK066 is a potent inhibitor of the sodium glucose co-transporters 1 and 2 (SGLTs) that decreases absorption of glucose in the gut and reabsorption in the kidney (Chao and Henry 2010). In the normal state, 90% of the filtered glucose is reabsorbed by SGLT2 in the proximal convoluted tubule cells of the kidney, with the remaining 10% reabsorbed by the SGLT1. Inhibition of SGLT2 results in benign glucosuria, decreased blood glucose and modestly lower body weight in healthy subjects and patients with T2DM (Bays 2013). In addition to expression in the kidney, SGLT1 is also expressed in the small intestine where it is required for glucose and galactose absorption. Inhibition of enteric SGLT1 results in glucose and galactose malabsorption (Turk et al 1991) which results in calorie wasting and other potential endocrine-based weight loss mechanisms. Combined SGLT1 and SGLT2 inhibition therefore offers the potential for improved efficacy over SGLT2 selective inhibitors in both lowering blood glucose and body weight.

LIK066 is an investigational dual SGLT1/2 inhibitor which is being developed as a novel treatment for obesity. Single and multiple doses of LIK066 induced glucosuria in healthy volunteers (HVs) and patients with T2DM, and significantly lowered glucose area under the time-concentration curve (AUC) after an oral glucose tolerance test (OGTT) in patients with T2DM. LIK066 was found to be safe and tolerated, had a favorable pharmacokinetic profile, and resulted in up to 3% placebo-adjusted weight loss over just 2 weeks in both healthy subjects and patients with T2DM. LIK066 at 150 mg daily dose (as qd, bid or tid) results in a significant

weight loss in obese patients (~ 6%) after 12 week treatment. Furthermore, twelve week treatment with LIK066 at 150 mg qd in normoglycemic and dysglycemic subjects was generally safe and well tolerated with diarrhea observed as a dose-limiting toxicity.

This study is a non-confirmatory, proof of concept study and is planned to assess the safety, tolerability and effect of LIK066 on serum ALT levels after 12 weeks of treatment with either LIK066 (150 mg OR 30 mg once daily) or placebo in either overweight or obese patients with type II diabetes mellitus (T2DM) OR patients with histologic evidence of NASH based on liver biopsy and elevated ALT levels.

Commercially Confidential Information

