6.6 Permitted dose adjustments and interruptions of study treatment

Investigational treatment dose adjustments and/or interruptions are not permitted.

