6.9 Recommended treatment of adverse events

Treatment of AEs may be considered at the discretion of the Investigator. Medication used to treat AEs must be recorded on the Concomitant medications/Significant non-drug therapies CRF. In case of intolerable diarrhea, see SOM for guidelines on management of diarrhea.

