7.2 Discontinuation of study treatment

Discontinuation of study treatment for a patient occurs when study treatment is stopped earlier than the protocol planned duration. Discontinuation of study treatment can be decided by either the subject or the investigator.

Study treatment must be discontinued under the following circumstances:

- Patient decision - patients may choose to discontinue study treatment for any reason at any time.
- The investigator believes that continuation would negatively impact the safety of the patient or the risk/benefit ratio of trial participation.
- Any protocol deviation that results in a significant risk to the patient's safety
- Pregnancy (see [Section 8.6](#) (Safety) and [Section 9.6](#) (Pregnancy reporting))
- Discontinuation may be considered when patients have to be treated by prohibited medications on a case by case basis.

- Use of prohibited treatment as per recommendations in [Table 5-1](#)
- Hypersensitivity (CTCAE grade 2 or higher) reaction to LIK066 requiring intervention.
- Clinically significant diarrhea, suspected to be related to the study drug and not responsive to recommended management per SOM that may put the patient at risk (identified by investigator after consultation with the sponsor)
- Symptomatic orthostasis confirmed by repeated orthostatic blood pressure changes (more than a 20 mmHg drop in systolic or 10 mmHg drop in diastolic blood pressure and increase in heart rate >20 bpm (compared to sitting results) when blood pressure and pulse are taken after at least 3 minutes (standing)
- Clinically significant urinary tract or genitourinary infections, at the discretion of the investigator and consultation with the sponsor
- Clinically symptomatic hypoglycemia confirmed by repeated blood glucose levels (<56 mg/dL)
- Ketoacidosis (symptoms of ketoacidosis include nausea, vomiting, abdominal pain, unusual tiredness and trouble breathing) confirmed by blood pH and ketones.
- For ALT, AST, total bilirubin and/or alkaline phosphatase elevations mandating study treatment discontinuations, please refer to [Section 9.3](#) and [Table 9-1](#) and [Table 9-2](#) for further instructions and monitoring. Of note, ALT and AST are abnormal at baseline in this study. Thus only elevation to >2X of the baseline value will trigger events listed in [Section 9.3](#).
- Adverse events, abnormal laboratory values or abnormal test result that indicate a safety risk to the patient, in the opinion of the investigator

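### Section 7.2 gives no single consequence when a patient takes a Table 5-1 antidiarrhoeal for drug-related diarrhea: one bullet requires a permanent stop, another leaves it to case-by-case judgement

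*Protocol*

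**What the plan says.** **The ban.** Protocol Section 5.2, Table 5-1, lists "Treatment with drugs that alter intestinal motility (e.g. erythromycin, metoclopramide, tegaserod, methylnaltrexone, alvimopan, loperamide, diphenoxylate and atropine (Lomotil" and also difenoxin with atropine. The period is "From 7 days prior to screening to EOS visit". The row makes no exception for treating an adverse event.

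**The stopping rules.** Section 7.2 opens its list with "Study treatment must be discontinued under the following circumstances". Three bullets under that heading bear on this point:

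- "Use of prohibited treatment as per recommendations in" Table 5-1.
- A separate bullet makes discontinuation optional, on an individual basis, for patients who need a prohibited medication.
- "Clinically significant diarrhea, suspected to be related to the study drug and not responsive to recommended management per SOM", with the further condition that it may put the patient at risk.

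The glossary defines study treatment discontinuation as permanent. Section 6.6 adds: "Investigational treatment dose adjustments and/or interruptions are not permitted".

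**Treating adverse events.** Section 6.9 says "Treatment of AEs may be considered at the discretion of the Investigator" and refers intolerable diarrhea to the Site Operations Manual (SOM). Section 6.10 requires each concomitant drug to be checked against the prohibited list and sends doubtful cases to the sponsor. Under Sections 3.1 and 6.4 the sponsor is unblinded to every patient's assignment.

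**Diarrhea.** Section 1.1 reports "diarrhea observed as a dose-limiting toxicity" at 150 mg once daily over 12 weeks. Section 1.3.1 places the mainly diarrheal and gastrointestinal events in the groups on 150 mg a day or more. Section 3.3 calls diarrhea the primary adverse event of the earlier 12-week study in obese patients, and says that it caused no treatment discontinuations or withdrawals there.

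**The concern.** The drugs in question treat the study drug's own main side effect, so the situation is foreseeable. Two bullets under one heading then give different answers, and neither says when it yields to the other. Because discontinuation is permanent and Section 6.6 rules out interruption, there is no stated middle course for diarrhea.

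Two sites with the same patient could act differently, each with support in the text. If the sponsor is consulted, the adviser knows the arm. If diarrhea is commoner at 150 mg, as the earlier data suggest, stops arising this way could also be commoner there. That would blur the comparison of 150 mg with 30 mg and placebo, both for tolerability and for endpoints measured at the end of treatment.

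**Working it through.** The plan states no figure for this point, so the check is a comparison of passages followed by an illustration of scale.

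**1. Where the rules diverge**

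| Patient with suspected drug-related diarrhea | 7.2 diarrhea bullet | 7.2 Table 5-1 bullet | 7.2 case-by-case bullet | Result |
|---|---|---|---|---|
| Managed without a listed drug (for example the carbohydrate reduction allowed in 5.3), responds | not met | not met | not met | continues; no conflict |
| Takes a listed antidiarrhoeal; diarrhea bullet not satisfied | not met | stop | stop or continue | **undetermined** |
| Clinically significant, unresponsive to SOM management, patient at risk | stop | stop if a listed drug was taken | stop or continue if a listed drug was needed | stops under the diarrhea bullet |

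The conflict is confined to the middle row. Whether the SOM leads patients into that row cannot be seen, because the SOM is not among the documents.

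**2. What a stop costs in data**

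- Section 7.2: a patient who stops treatment is not withdrawn unless consent is withdrawn, and should return for scheduled assessments where possible. ALT and weight can still be collected, but off treatment.
- Table 8-1, footnote 17: after an early stop, the MRI is done at the end-of-study visit.
- Section 8.5.5: the end-of-treatment MRI is not done if treatment stops before Week 8. Liver fat is therefore the most exposed endpoint.

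**3. Scale**

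- Arm sizes: 33 patients at 2:1 give 22 on 150 mg and 11 on placebo. The remaining 77 at 2:4:1 give 22, 44 and 11. The sums are 44 (150 mg), 44 (30 mg) and 22 (placebo), matching Figure 3-1.
- Formula under the strict reading: stops = arm size × share of the arm taking a listed antidiarrhoeal.
- The documents give no such shares. Those below are assumptions and include zero, in view of Section 3.3.

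| Assumed share, 150 mg / 30 mg / placebo | Stops, 150 mg / 30 mg / placebo | Total of 110 | 150 mg minus placebo |
|---|---|---|---|
| 0 / 0 / 0% | 0 / 0 / 0 | 0 | 0 points |
| 5 / 0 / 0% | 2.2 / 0 / 0 | 2.2 | 5 points |
| 10 / 5 / 0% | 4.4 / 2.2 / 0 | 6.6 | 10 points |
| 20 / 5 / 5% | 8.8 / 2.2 / 1.1 | 12.1 | 15 points |
| 30 / 10 / 5% | 13.2 / 4.4 / 1.1 | 18.7 | 25 points |

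Under the case-by-case reading, the count for each row could be anything from zero to the figure shown. The text does not fix it.

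**The case against.** Much of the case on the other side stands, and it rules out several stronger readings that a reader might infer.

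- **That one loperamide tablet always ends treatment.** The case-by-case bullet and Section 6.10 both allow continuation. One could try to harmonise the bullets by applying the optional one to necessary use and the compulsory one to other use. The text does not draw that line, so the conflict remains.
- **That Section 6.9 contradicts Table 5-1.** The investigator's discretion is bounded by the check against prohibited medication in Section 6.10. Discretion among permitted drugs is coherent.
- **That the diarrhea bullet is an opposite rule, so worse untreated diarrhea must continue.** It is one trigger among several. Section 7.2 also requires a stop when the investigator judges that continuing would harm the patient's safety, or that an adverse event signals a safety risk.
- **That arm-dependent discontinuation will follow.** Section 3.3 reports no discontinuation for diarrhea, and Section 1.3.1 reports no LIK066-related withdrawals from treatment for adverse events. This evidence lowers the expected size. It does not settle the matter, since the documents do not say whether the earlier study had the same ban and stopping rule.
- **That diarrhea would be misrecorded as a prohibited-medication stop.** The investigator determines the primary reason, and the documents show no CRF options. Diarrhea is also captured as an adverse event, and SAP Section 7.2 tabulates adverse events by treatment, with separate tables by grade and drug relationship.
- **That these stops use up the allowance for non-completion.** Section 4 expects at least 88 of 110 to complete, so 1 − 88/110 = 20%, or 22 patients. A treatment stop is not a study withdrawal, so the two counts should not be set against each other.

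**Conclusion.** The conflict within Section 7.2 is in the text and needs no assumption. For a patient given a listed antidiarrhoeal for suspected drug-related diarrhea, the protocol supports both a permanent stop and continuation, even when the diarrhea bullet is not met. It matters because this is the drug's primary adverse event, it appears dose-related, and the party consulted in doubtful cases is unblinded.

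The consequence is a risk of inconsistent and possibly arm-related stops, not a demonstrated bias. Its size is unknown. Under the assumed shares it runs from 0 to about 13 of 44 patients at 150 mg and from 0 to about 19 of 110 overall, on the strict reading only. The primary endpoint can still be measured after a stop; liver fat is lost when the stop comes before Week 8. Missing-data handling is redacted, so the effect on the analyses cannot be judged. This should be corrected, but it does not by itself put the primary analysis in doubt.

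**What to change.** 1. Reconcile Table 5-1, the two prohibited-treatment bullets and the diarrhea bullet in Section 7.2, Section 6.9 and the SOM, so that use of an antidiarrhoeal for suspected drug-related diarrhea has one stated consequence. Which passage governs is for the medical team to decide.
2. Add one SAP table giving, by arm, the treatment stops in which a prohibited drug was taken for diarrhea. Derive it from the adverse event, concomitant medication and Dosage Administration CRFs. Leave the investigator's recorded primary reason as it is; the table is an additional count, not a reclassification.

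The cost is wording in Sections 5.2, 6.9 and 7.2 and in the SOM, plus one table. It needs no extra patients, visits, procedures or data collection.
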